Furthermore, olanzapine may also have effects on gut neurohumoral signaling that are important in regulation of appetite and weight. Long-term use of olanzapine between 26 and 52 weeks has been shown to increase plasma levels of ghrelin in mouse models as well as humans on long-term treatment for schizophrenia [32-34]. However, short-term use between 2 to 9 weeks may actually decrease levels of ghrelin [35-37]. Ghrelin is a hormone that is produced by the gut, stimulates appetite, and has been shown to improve symptoms as well as promote gut motility in gastroparesis [38-40]. Previous data have shown that olanzapine may affect only ghrelin levels whereas other gut hormones, e.g. peptide YY, pancreatic polypeptide, leptin and GLP-1 were not affected [34, 37]. Because of this data as well as limited resources, only ghrelin is going to be evaluated during this study.

There are few options currently that are efficacious and safe for the treatment of gastroparesis and development of other therapeutic options is needed. Furthermore, in patients with severe gastroparesis causing anorexia and weight loss, polypharmacy is often needed to stimulate appetite and alleviate symptoms. Olanzapine may possess unique properties, which makes it a potentially attractive therapeutic option for gastroparesis. We hypothesize that olanzapine will be effective and safe in controlling symptoms as well as stimulate appetite in gastroparesis. We also hypothesize that olanzapine will promote gastric motility. Finally, we hypothesize that olanzapine will stimulate the secretion of ghrelin, thereby aiding in the treatment of gastroparesis. This pilot study may provide further insight into the efficacy and safety of olanzapine in gastroparesis, which could be utilized in a larger randomized, placebo-controlled prospective study in the future.

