2 OBJECTIVES

Aim 1: Investigate the efficacy and safety of olanzapine in the treatment of nondiabetic gastroparesis.

We will utilize the gastroparesis cardinal symptom index daily diary (GCSI-DD) and an appetite visual analog scale (VAS) to compare severity of symptoms before and after treatment with olanzapine. Subjects will undergo regular testing of blood glucose, insulin, hemoglobin (Hgb) A1c, body mass index (BMI), liver enzymes, thyroid stimulating hormone (TSH), and prolactin levels during the study as well as after treatment completion to determine the safety of the medication. All adverse events will be compiled to investigate the tolerability of the medication.

Aim 2: Determine whether olanzapine has prokinetic effects on gastric emptying in gastroparesis.

We aim to test gastric motility, including gastric emptying and antroduodenal contractility parameters, by wireless motility capsule (WMC) before and at the completion of the study to determine if olanzapine has any pro-motility effects in gastroparesis.

Aim 3: Examine the effects of olanzapine on neurohumoral regulation of eating and appetite.

We seek to determine whether olanzapine promotes secretion of ghrelin in gastroparesis.

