6 STUDY DESIGN AND PROCEDURES

This is a pilot study of 10 consecutive subjects ages 18 – 80 with documented delayed gastric emptying within the past 2 years and history of nausea, vomiting, bloating, anorexia, early satiation, post-prandial fullness, and weight loss for at least 6 months without structural or organic cause will be enrolled. This will be an open label trial without a placebo arm to determine efficacy and safety of the medication in this population. This will be a single center study with subjects being enrolled at the University of Michigan. [name] at Massachusetts General Hospital will act as a co-I and will assist with data analysis but will not enroll any patients. [name] will receive only de-identified information.

The study will consist of a screening/baseline period of up to 30 days, an 8-week treatment period, and a 14-day post treatment safety follow-up visit and assessment of symptoms.

Screening/Baseline:

Subjects will participate in a screening/baseline visit within 30 days prior to study dosing. Subjects will be instructed to fast prior to the screening visit at which time they will undergo blood sampling for complete blood count (CBC), complete metabolic panel (CMP), lipid profile, insulin, Hgb A1c, prolactin, TSH, and urine or blood pregnancy screen (if applicable). A baseline ECG will also be performed. Ghrelin levels will be measured. Baseline vital signs, height, weight, and BMI will also be calculated. They will also have their gastric emptying assessed by wireless motility capsule (WMC). To be eligible for the study, the subjects' gastric emptying time, as determined by WMC, needs to be greater than 5 hours. Potential subjects will complete the gastroparesis cardinal symptom index daily diary (GCSI-DD) evaluation, appetite visual analog score (VAS), and Bristol Stool Form Scale (BSFS) for a minimum of 7 days to determine baseline level of symptoms [41]. Questionnaires will be completed in the evening after dinner. Mean total GCSI-DD score must be ≥ 2 in order to qualify for the study.

Week 1 – Week 8:

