The purpose of this study is to ensure that severe complications to olanzapine in gastroparesis are rare and to see whether olanzapine might improve symptoms in gastroparesis. We will treat ten patients with gastroparesis. The trial will stop if any SAE related to the drug is encountered.

Study Timeline:

Figure 1 Gastroparesis Subject Timeline

7 Data Collection and Management Procedures

Data Handling and Entry: All data including questionnaire results and physiologic testing will be recorded and reviewed by the study team. Data will then be entered into an electronic case report form (eCRF) that complies with Title 21 of the Code of Federal Regulations (21 CFR Part 11). All passwords will be strictly confidential to protect subject's protected health information (PHI). Only the Primary Investigator (PI) and Study Coordinator will have access to the data and subject identifiers. Only the PI and Study Coordinator will be allowed to enter data onto the password-protected web-based server.

Computer Systems: Data entry will be entered into REDCAP which is validated and conforms to regulatory requirements. Only the Primary Investigator (PI) and Study Coordinator will have access to the data and subject identifiers. Only the PI and Study Coordinator will be allowed to enter data onto the password-protected web-based server.

Data Validation: Validation checks will be programmed within the eCRF system as well as supplemental validation performed by review of the downloaded data, will be applied to the data in order to ensure accurate, consistent, and reliable data.

Direct Access to Source Data: A developed review procedures that complies with Good Clinical Practice (GCP) guidelines.

Source Document/Case Report Form Completion: Source documents and the eCRFs will be completed for each study patient. It is the Investigator's responsibility to ensure the accuracy, completeness, and timeliness of the data reported in the patient's source document/eCRF. The source document/eCRF should indicate the patient's participation in the study and should document the dates and details of the study procedures, AEs, and patient status.

Record Retention: The Investigator will maintain all study records according to applicable regulatory requirement(s).

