8 DATA ANALYSIS

Procedure for Accounting for Missing, Unused, and Spurious Data: The primary outcome measure in our study is whether olanzapine is efficacious and safe for the treatment of idiopathic gastroparesis. We will use multiple imputation with 10 imputed datasets to replace missing values on outcome and predictor variables [46]. If 10 imputed datasets are not sufficient to ensure stability of estimates, we will use 20 imputed datasets. This allows for maximal use of available data while maximizing statistical power.

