10 STATISTICAL CONSIDERATIONS

Changes in measures from baseline will first be examined using descriptive statistics and graphical analysis. Significance of changes by the post treatment assessment will be determined using paired t tests or Wilcoxon rank sum tests, depending on the normality of the measures. Hierarchical regression will be used to analyze patterns of change across all measurement times, with time as a nested factor within subject. Adverse events will be summarized by proportions and 95% confidence intervals.

Sample size was based on variance estimates from prior studies using GCSI-DD and the appetite VAS in patients with gastroparesis [41, 47], and was computed using a 2-

sided type I error rate of 0.05. Conservatively using the largest variance reported for any of the GSCI subscales, and conservatively using a within-subject correlation of 0.6, a sample size of 10 patients will provide 88% power to detect a 1-point decrease in GCSI-DD, which we judged to be a clinically meaningful change in the subscales and total scale. For a more likely within-subject correlation of 0.8, power would be >99%. For the appetite VAS, we judged a 10 mm change to be clinically significant. Again conservatively using the largest of the reported variances, 10 patients will give 80% power to detect a 10mm change if the within-subject correlation is 0.6 and 97% power if the within-subject correlation is 0.8. A sample size of 10 subjects will also provide sufficient precision in parameter estimates from this study for use in power calculations for future studies of olanzapine in patients with gastroparesis.

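### The stated purpose of ensuring that severe complications are rare is more than ten subjects can show: even 0 events in 10 leaves an exact 95% upper limit of 31%

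*Combined protocol and SAP*

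**What the plan says.** The sentence at issue stands once, under Stopping Criteria in Section 6: "The purpose of this study is to ensure that severe complications to olanzapine in" gastroparesis are rare, with a second purpose of seeing whether symptoms might improve. The means follow directly: "We will treat ten patients with gastroparesis. The trial will stop if any SAE related to the drug is encountered". Section 6 also describes the design: "This will be an open label trial without a placebo arm to determine efficacy and safety of the medication in this population".

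Other sections are both weaker and stronger on safety:

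- Section 2, Aim 1, is modest: "Investigate the efficacy and safety of olanzapine in the treatment of nondiabetic gastroparesis".
- Section 1 is modest too: "This pilot study may provide further insight into the efficacy and safety of olanzapine in gastroparesis". It looks ahead to a larger randomised, placebo-controlled study.
- Section 8 is stronger: "The primary outcome measure in our study is whether olanzapine is efficacious and safe for the treatment of idiopathic gastroparesis".

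Section 10 justifies the sample size on efficacy: "a sample size of 10 patients will provide 88% power to detect a 1-point decrease in GCSI-DD", and for appetite "10 patients will give 80% power to detect a 10mm change", both at a within-subject correlation of 0.6. It adds that ten subjects will give parameter estimates precise enough to plan later studies. For adverse events it plans proportions with 95% intervals but names no interval method. No section defines *rare*, gives an expected or acceptable rate of serious events, or states what ten subjects can show about them.

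**The concern.** A purpose is what a reader holds the result against. If the purpose is to ensure that severe complications are rare, a trial that treats all ten subjects without stopping will seem to have achieved it. Whether that is warranted depends on how high the true rate could be when nothing is seen in ten people, and the plan gives no figure for this.

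Two things are at stake. Section 8 makes safety part of the primary outcome, and Section 1 intends the results for use in a larger trial. A clean result read as evidence of rarity would carry more weight in planning that trial than ten subjects can bear.

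**Working it through.** **The plan's own figures.** There is no safety figure to reproduce. The efficacy powers cannot be reproduced directly because the variances are not given, but they can be checked against each other. Take a paired t test with n = 10, two-sided 0.05, and SD of change = SD × √(2(1 − ρ)).

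- GCSI-DD: 88% power for 1 point at ρ = 0.6 implies an SD of change of 0.896, so SD = 0.896/√0.8 = 1.00. At ρ = 0.8 this gives 99.3% (plan: above 99%).
- Appetite VAS: 80% power for 10 mm at ρ = 0.6 implies an SD of change of 10.04 mm, so SD = 11.2 mm. At ρ = 0.8 this gives 97.6% (plan: 97%).

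These figures are coherent, but none of them concerns serious events.

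**Inputs for the safety check.** n = 10 (Section 6); 95% confidence (Section 10); best possible count = 0. Subjects are treated as independent with a common event probability p.

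**Upper limit after 0 events in n.**

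- Exact two-sided: 1 − 0.025^(1/n) = 1 − 0.025^(1/10) = 0.308, so the interval is 0 to 31%.
- Exact one-sided: 1 − 0.05^(1/10) = 0.259.
- Wilson: 1.96²/(10 + 1.96²) = 0.278.
- Rule of three: 3/10 = 0.30.
- Normal approximation: 0 ± 1.96 × √(0 × 1/10) = 0 to 0%, which is uninformative.

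Every usable method gives between 26% and 31%.

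**Chance of seeing no event, (1 − p)^10.**

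| True rate p | P(0 of 10) |
|---|---|
| 1% | 90% |
| 2% | 82% |
| 5% | 60% |
| 10% | 35% |
| 20% | 11% |

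Seeing at least one event is more likely than not only when p exceeds 1 − 0.5^(1/10) = 6.7%. An 80% chance of seeing one needs p = 1 − 0.2^(1/10) = 14.9%.

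**Role of the stopping rule and the single arm.** A result of 0 of 10 can arise only if the trial never stopped, so the fixed-sample limit holds unchanged under the rule. A placebo arm does not enter any of the formulas above. Only n matters.

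**Which event is meant.** The purpose speaks of severe complications. The stopping rule uses drug-related SAEs, with SAE defined in Section 6 and again in Section 11.3. Section 11.3 separately grades a severe adverse event as grade 3, by inability to carry on normal activities and need for professional medical attention. These sets overlap but differ. The arithmetic applies to whichever is chosen, provided it is counted once per subject and none occurs.

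**The case against.** The strongest reply is that this is one loose sentence in a pilot. It introduces the stopping rule, where *ensure* may mean protecting subjects rather than proving a rate. The formal aim is only to investigate safety, Section 1 promises no more than further insight, and Section 10 already plans intervals that would show the uncertainty. No hypothesis, threshold or success rule is tied to rarity.

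Most of this stands, and it keeps the point small. It does not remove it. The sentence names the purpose of the study, not of the stopping rule, and an interval reported afterwards does not correct a purpose stated beforehand. Even on the protective reading, a true rate of 10% leaves the rule untriggered 35% of the time.

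A reader might infer stronger things that the documents do not support:

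- *That the single arm or the stopping rule is at fault.* Neither affects the 31%.
- *That the investigators will present 0 of 10 as proof of rarity.* No section says so.
- *That the normal approximation will be used.* Section 10 is silent on method.
- *That dropout will widen the interval.* With nine or eight evaluable subjects the exact limit would be 33.6% or 36.9%, but those denominators are assumptions. The plan gives no dropout rate, and Section 6 provides safety contact within two weeks for anyone who discontinues.
- *That all the safety data are this weak.* The calculation concerns event counts, not the repeated glucose, weight and laboratory measures.

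**Conclusion.** The point holds as an overstated purpose, not as a design defect. With ten subjects the best attainable result is compatible with a true event rate of up to 31% (26% to 31% across the usable methods). No definition of *rare* is needed to conclude that this falls short of it.

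The conclusion assumes that all ten subjects are evaluable, that they are independent with a common event probability, and that the count refers to the planned eight weeks of treatment plus 14 days of follow-up. It does not depend on which of the three event definitions is adopted.

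A reader might go on to infer that the trial is too small and should be enlarged. The documents do not support that: they set no target for the event rate, and the pilot aims in Sections 1 and 2 do not require one. The point is minor and interpretive, worth correcting because the correction is nearly free.

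**What to change.** 1. In Section 6, Stopping Criteria, restate the purpose along these lines: *to obtain preliminary safety data on olanzapine in gastroparesis, and to look for signs of symptom improvement*. Name the event that will be counted, for example the drug-related SAE as defined in Sections 6 and 11.3, so that severe complication, SAE and grade 3 event are not used interchangeably.
2. In Section 10, add: *If 0 of 10 subjects have such an event, the exact 95% confidence interval is 0 to 31%; the trial cannot establish that such events are rare.*
3. In Section 10, state that the adverse event intervals already planned will use an exact or Wilson method, since the normal approximation gives 0 to 0% for a zero count.
4. State that *safety* in the Section 6 design statement and *safe* in the Section 8 primary outcome are meant in the same limited sense.

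Sample size, visits, endpoints and stopping rule are unchanged. The cost is a few sentences and a less favourable safety statement.

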8 DATA ANALYSIS

Procedure for Accounting for Missing, Unused, and Spurious Data: The primary outcome measure in our study is whether olanzapine is efficacious and safe for the treatment of idiopathic gastroparesis. We will use multiple imputation with 10 imputed datasets to replace missing values on outcome and predictor variables [46]. If 10 imputed datasets are not sufficient to ensure stability of estimates, we will use 20 imputed datasets. This allows for maximal use of available data while maximizing statistical power.

9 QUALITY CONTROL AND QUALITY ASSURANCE

The PI and Study Coordinator will be responsible for Quality Control and Quality Assurance and will be performed in accordance with Standard Operating Procedures at the University of Michigan.

10 STATISTICAL CONSIDERATIONS

Changes in measures from baseline will first be examined using descriptive statistics and graphical analysis. Significance of changes by the post treatment assessment will be determined using paired t tests or Wilcoxon rank sum tests, depending on the normality of the measures. Hierarchical regression will be used to analyze patterns of change across all measurement times, with time as a nested factor within subject. Adverse events will be summarized by proportions and 95% confidence intervals.

Sample size was based on variance estimates from prior studies using GCSI-DD and the appetite VAS in patients with gastroparesis [41, 47], and was computed using a 2-

sided type I error rate of 0.05. Conservatively using the largest variance reported for any of the GSCI subscales, and conservatively using a within-subject correlation of 0.6, a sample size of 10 patients will provide 88% power to detect a 1-point decrease in GCSI-DD, which we judged to be a clinically meaningful change in the subscales and total scale. For a more likely within-subject correlation of 0.8, power would be >99%. For the appetite VAS, we judged a 10 mm change to be clinically significant. Again conservatively using the largest of the reported variances, 10 patients will give 80% power to detect a 10mm change if the within-subject correlation is 0.6 and 97% power if the within-subject correlation is 0.8. A sample size of 10 subjects will also provide sufficient precision in parameter estimates from this study for use in power calculations for future studies of olanzapine in patients with gastroparesis.

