Subjects will initially start on olanzapine 2.5 mg by mouth daily to be taken at bedtime. Subjects will return on days 7 and 14 to determine response to medication. Medication dose can be increased to 5 mg on day 7 and 10 mg on day 14, respectively, based on incomplete symptom response, which is defined as a mean change in GCSI-DD score < 0.5 from baseline. Height and weight will be measured on Day 7. The total dose of olanzapine will not exceed 10 mg daily during this study. Subjects will be monitored for adverse events and undergo blood sampling for glucose, insulin, and Hgb A1c on day 14. Vital signs, height, weight, and BMI will also be evaluated. Subjects will be instructed to bring their study medication with them on day 14 for assessment of study drug accountability.

Subjects will be contacted by phone at least once within 2 weeks following the day 14 visit to assess for potential side effects. Subjects may also come in for an extra/optional study visit between the Day 14 and Day 35 visits, if warranted by side effects.

Subjects will return on day 35 to monitor for adverse events, vital signs, height, weight, BMI, and glucose check.

During the study, subjects will rate their gastroparesis symptoms on a daily basis by completing the GCSI-DD and appetite VAS questionnaires. Subjects will also record daily the number of stools and their consistency [42]. Subjects will be asked to complete all diaries after the evening meal. The subjects will fast prior to returning to clinic on the morning of day 56 to undergo assessment of their gastric emptying time by WMC and complete an appetite VAS. Blood sampling for LFTs, glucose, insulin, Hgb A1c, and ghrelin levels will be performed. Vital signs, height, weight, and BMI will also be measured. All remaining study medication will be returned to the clinical unit for final drug accountability. Subjects will continue to rate their gastroparesis symptoms for 14 days following the end of dosing.

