Post-Treatment Assessment:

At the conclusion of 56 days of dosing, subjects will return for a follow-up visit 14 days (+ 2 days) after the last dose of study medication. All subjects will have blood sampling for CBC, CMP, lipid profile, TSH, prolactin, insulin, Hgb A1c, and ghrelin. Height, weight, and BMI will be calculated. One final appetite VAS will be completed. The duration of each patient's participation in the study from screening to follow-up visit will be approximately 14 weeks.

Subjects are free to discontinue participation in the study at any point. If a subject decides to prematurely discontinue from the study, they will be contacted within two weeks for safety follow-up visit(s). Reasons for withdrawal will be documented by the PI. If the reason for removal of a subject from the study is an AE, the principal specific event will be recorded on the CRF. The subject will be followed until the AE is resolved.

Gastric Motility:

Gastric motility will be tested by using the WMC wireless capsule system (The SmartPill Corporation, Buffalo, NY). This offers a potentially more complete examination into possible etiologies for gastroparesis including delayed gastric emptying as well as gastric and small bowel contractility abnormalities. We will follow the protocol for measuring gastric emptying by wireless motility capsule as described previously in the literature [43]. Gastric emptying time (GET) is defined as the duration of time from capsule ingestion to entry of the capsule into the duodenum. Subjects will swallow the WMC capsule with 50 ml of water followed by ingestion of a standardized meal comprising of a nutrient bar, which has a total caloric value of 255 kcal (72%)

carbohydrate, 24% protein, 2% fat, and 2% fiber) [44]. Because of the low risk of capsule retention especially once the capsule enters the colon, plain abdominal radiograph (KUB) will be performed only if there is no documentation of the capsule passing the ileocecal valve and the patient has symptoms of capsule retention. Pressure data recorded by the WMC capsule will be analyzed for 1 hour before and after the WMC empties the stomach (GET). The analyzed parameters are: number of contractions (Ct), and motility index defined as: MI = Ln (sum of pressure amplitudes * number of contractions +1) [45].

Stopping Criteria:

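### Section 10 ties the paired tests of change to the post-treatment assessment, Section 6's name for a visit two weeks off drug with no capsule test; the end-of-treatment comparison should be stated

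*Combined protocol and SAP*

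**What the plan says.** Section 10 gives one time point for its paired tests: "Significance of changes by the post treatment assessment will be determined using paired t tests", or a Wilcoxon test if the measure is not normal. No measure is assigned to another visit, and no diary window is defined.

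In Section 6, Post-Treatment Assessment is the subheading for the visit at which "subjects will return for a follow-up visit 14 days (+ 2 days) after the last dose of study medication". The design summary in the same section uses the term in the same sense: "an 8-week treatment period, and a 14-day post treatment safety follow-up visit and assessment of symptoms".

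The end-of-treatment visit is described separately, under Week 1 – Week 8. Subjects return fasting on the "morning of day 56 to undergo assessment of their gastric emptying time by WMC and complete an appetite VAS". At that visit, "Blood sampling for LFTs, glucose, insulin, Hgb A1c, and ghrelin levels will be performed". After dosing stops, "Subjects will continue to rate their gastroparesis symptoms for 14 days following the end of dosing".

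Section 10 also plans descriptive and graphical summaries and a hierarchical regression over every measurement time.

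**The concern.** Section 1 hypothesises that olanzapine controls symptoms, stimulates appetite, promotes gastric motility and stimulates ghrelin secretion. These are statements about the effect of the drug. A paired test of baseline against a visit two weeks after the last dose compares two states without olanzapine. It asks whether a change persists after stopping.

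Timing matters particularly for ghrelin. Section 1 itself reports that levels may fall with 2 to 9 weeks of use and rise with 26 to 52 weeks, so values on drug at 8 weeks and off drug two weeks later need not answer the same question.

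As written, two analysts could run the planned paired tests on different data and both claim to follow the plan. In an open-label study the choice could also be made after the results are known. A benefit present only during dosing could be missed by the named test.

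**Working it through.** No arithmetic decides this point. The check is to set the schedule in Section 6 against the time point in Section 10.

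**Step 1: what the visit name means.** Section 6 attaches it to the visit 14 to 16 days after the last dose. If the last dose is on Day 56, that is Day 56 + 14 = 70 to Day 56 + 16 = 72. The design summary places the post-treatment follow-up after the 8-week treatment period. No readable passage uses the term for Day 56.

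**Step 2: what is available at each time.**

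| Measure | Baseline | End of treatment | Off-drug follow-up | Literal Section 10 test |
|---|---|---|---|---|
| GCSI-DD | Diary, at least 7 days | Daily diary | Symptom ratings for 14 days | Off drug, window not stated |
| Appetite VAS | Diary, at least 7 days | Daily diary and Day 56 | One final VAS at the visit | Off drug |
| Ghrelin | Screening | Day 56 | Yes | Off drug |
| Capsule measures | Screening | Day 56 | Not listed | No data |
| CBC, lipids, TSH, prolactin | Screening | Not listed | Yes | Off drug, the only post-baseline draw |

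The blood tests come from three lists in Section 6. Screening has "blood sampling for complete blood count (CBC), complete metabolic panel (CMP), lipid profile, insulin, Hgb A1c, prolactin, TSH", with ghrelin listed separately. Day 56 has the shorter list quoted above. At follow-up: "All subjects will have blood sampling for CBC, CMP, lipid profile, TSH, prolactin, insulin, Hgb A1c, and ghrelin".

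**Step 3: what follows.**
- Day 56 together with the daily diary covers every efficacy and mechanism measure: GCSI-DD, VAS, capsule and ghrelin.
- The follow-up visit covers all of these except the capsule, so the literal rule cannot be carried out for Aim 2.
- The four safety tests in the last row have one post-baseline draw each, so their time point is not in doubt.
- For GCSI-DD the literal reading is also incomplete. The scale is a daily diary and is not listed as a procedure at the follow-up visit, so a window has to be chosen under either reading.

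**Step 4: does anything else settle it?**
- Section 8 describes the primary outcome as efficacy and safety, without a measure or a time.
- Aim 1 compares symptoms before and after treatment, which fits either reading.
- Aim 2 places the second capsule test at study completion, yet the schedule puts it on Day 56, before the follow-up visit.
- The regression uses on-drug data but names no visit or contrast.
- The Figure 1 timeline could not be read.

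**The case against.** The best defence is that the phrase is loose wording for end of treatment. Section 10 says change *by* that assessment, not *at* it. The literal reading would leave Aim 2 without a paired test, which the authors can hardly have intended. Aim 2's own description of the second capsule test shows that time points are worded loosely elsewhere. Fasting is specified for screening and Day 56 but not for follow-up, which makes Day 56 the natural match for ghrelin and the capsule. The follow-up is labelled a safety visit, although symptom assessment is added to it.

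Much of this stands. It makes Day 56 the likelier intention, but it remains inference: the only meaning that the readable text gives to the term is the off-drug visit.

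Two stronger readings are tempting. A reader might infer that every significance test is fixed off drug. The documents do not support that: the time point governs only the paired t and Wilcoxon tests, and the regression covers the treatment period. A reader might also infer that no single visit can serve the trial's aims. That is true only if the safety blood tests are counted, since Day 56 with the diary serves every efficacy and mechanism measure.

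**Conclusion.** The point holds as a mismatch between a stated analysis rule and the trial's aims. Followed as written, the paired tests of GCSI-DD, appetite VAS and ghrelin are done off drug, and the capsule measures cannot be tested. It should be corrected before analysis.

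The consequence is limited. The trial is a 10-subject open-label pilot, no decision rule hangs on these tests, and the descriptive, graphical and regression analyses use on-drug data under either reading. A reader might want to express the harm as lost power. The documents do not allow that, because they give no figure for how much of an effect remains two weeks after stopping. The plan's stated power figures are not disputed here.

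The conclusion rests on the readable text. If Figure 1 labels Day 56 as the post-treatment assessment, the point reduces to aligning the terms and fixing the diary window.

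**What to change.** In Section 10, replace the single phrase with the following:

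1. **GCSI-DD and appetite VAS:** baseline diary mean against the mean of a prespecified final on-drug diary week. Days 49 to 55 would be one choice: seven days, matching the 7-day minimum at baseline and ending before the Day 56 morning visit. The window is the team's choice but must be fixed in advance.
2. **Capsule measures and ghrelin:** screening against Day 56.
3. **Regression:** name the contrast that matches the end-of-treatment comparison.
4. **Off-drug symptom, VAS and ghrelin values:** report separately as persistence after stopping.
5. **CBC, lipids, TSH and prolactin:** keep the follow-up visit, their only scheduled post-baseline draw, and label the result as off drug.

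The cost is a few sentences in Section 10 and minor analysis work. All the data are already scheduled, so no visit, test or subject is added.
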